### **10.5 Disposal, Return, or Retention of Unused Drug**

The study site staff or pharmacy personnel will retain all materials returned by the subjects' parents or legal guardians until the study monitor has performed drug accountability. At the end of the study, the study monitor will provide instructions as to the disposition of any unused investigational product. If the study monitor authorizes destruction at the study site, the investigator will ensure that the materials are destroyed in compliance with applicable environmental regulations, institutional policy, and any special instructions provided by Vertex. Destruction will be adequately documented.

### **10.6 Compliance**

Study drug accountability should be assessed at each visit by counting returned dosage units (sachets/packets).

If there is continued noncompliance with study requirements, restrictions, instructions, and study drug dosing despite educational efforts, the investigator should contact the Vertex medical monitor or authorized designee to discuss noncompliance and discontinuation of the subject from the study.

## **10.7 Blinding and Unblinding**

This will be an open-label study.

## **11 ASSESSMENTS**

### **11.1 Timing of Assessments**

The timing of assessments for the ivacaftor arm is shown in:

- [Table 3-1](#): subjects from Study 124 Part B who have a Same-day Transition (Section [9.1.1.2.1](#))
- [Table 3-2](#): subjects from Study 124 Part B who have a Gap Transition (Section [9.1.1.2.1](#))
- [Table 3-3](#): subjects from Study 124 Part A or subjects not from Study 124 Parts A or B

The timing of assessments for the observational arm is shown in [Table 3-4](#).

### **11.2 Subject and Disease Characteristics**

For subjects transitioning from Study 124 Part B, demographics, medical history, and historical data will be taken from Study 124. For all other subjects, demographics, medical history, length, weight, and the additional historical data described below will be collected before (e.g., at screening) or at Day 1.

The following historical data from birth to screening will also be collected:

- Maternal/pregnancy history: complications in pregnancy, gestational age at delivery, method of delivery
- Quarterly (approximately every 12 weeks) length and weight measurements
- The dates and reasons for all CF-related hospitalizations
- Any use (yes or no) of the following medications: inhaled tobramycin, inhaled aztreonam, inhaled colimycin, inhaled hypertonic saline, dornase alfa, ibuprofen, azithromycin, and pancreatic enzyme replacement therapy
- Historical pancreatic status measurements (prior fecal elastase-1 assessments)

### **11.3 Pharmacokinetics**

Not applicable.

### **11.4 Pharmacodynamics (Ivacaftor Arm Only)**

#### **11.4.1 Sweat Chloride**

Collection of sweat chloride samples will be performed at qualified study sites using an approved Macroduct® (Wescor, Logan, UT) collection device. Sweat chloride samples will be sent to a central laboratory for testing and interpretation of results. Individual sweat chloride test results will not be disclosed to the study sites. Specific instructions for the collection, handling,

processing, and shipping of sweat chloride samples to the central laboratory will be provided separately.

The sweat chloride test at the Day 1 Visit must be performed before the ivacaftor dose. Baseline sweat chloride test is not required at Day 1 if it was completed at screening. At subsequent visits through Week 24, the sweat chloride test must be performed within a window of  $\pm 2$  hours relative to the ivacaftor dose. After the Week 24 Visit, the sweat chloride test may be performed at any time during the visit. Change from baseline in sweat chloride will be analyzed as a secondary endpoint in this study.

## **11.5 Efficacy and Exploratory Assessments (Ivacaftor Arm Only)**

### **11.5.1 Measures of Nutritional Status**

Length and weight must be measured with the subject in a dry diaper or dry underclothes only. Length should be measured throughout the study while the subject is lying supine by measuring from the crown of the head to the bottom of the feet with the hips and legs straightened. Change from baseline in weight, length, weight-for-length, weight-for-age z-score, length-for-age z-score, weight-for-length-for-age z-score, BMI, and BMI-for-age z-score will be analyzed as a tertiary endpoint in this study.

### **11.5.2 Qualitative Microbiology Cultures**

A cotton-tipped swab will be used to collect the microbiology specimen from the posterior oropharyngeal wall and tonsillar pillars. Specific instructions for the collection, processing, and shipment of samples will be provided in a separate Laboratory Manual.

### **11.5.3 Pulmonary Exacerbations**

The incidence of pulmonary exacerbations will be recorded. For this study, given the absence of a consensus definition for pulmonary exacerbation in clinical studies in this population, 2 definitions will be applied to the signs and symptoms shown below for analyses of pulmonary exacerbations:

Definition 1: Treatment with oral, inhaled, or intravenous (IV) antibiotics **AND** fulfillment of 1 or more of the criteria from List A or List B, within 3 days before antibiotic start date through antibiotic stop date.

Definition 2: Treatment with oral, inhaled, or IV antibiotics **AND** fulfillment of 1 criterion from List A or 2 criteria from List B, within the period 3 days before antibiotic start date through antibiotic stop date.

The occurrence of any new or changed antibiotic therapy (IV, inhaled, oral) and the presence of the following signs and symptoms will be collected:

#### **List A:**

- Oxygen saturation  $<90\%$  on room air or  $\geq 5\%$  decrease from baseline
- New lobar infiltrate(s) or atelectasis on chest x-ray
- Hemoptysis (more than streaks on more than 1 occasion in the past week)

#### **List B:**

- Increased work of breathing or respiratory rate (duration  $\geq 3$  days)

- New or increased adventitial sounds on lung exam (duration  $\geq 3$  days)
- Weight loss of  $\geq 5\%$  from the highest value or decrease across 1 major percentile for age in the past 6 months
- Increased cough (duration  $\geq 3$  days)
- Worked harder to breathe during physical activity (duration  $\geq 3$  days)
- Increased chest congestion or change in sputum (duration  $\geq 3$  days)

#### **11.5.4 CF-related Hospitalizations**

Subject's parents/caregivers will be queried about CF-related hospitalizations. The dates and reasons for the CF-related hospitalizations will be collected.

#### **11.5.5 Markers of Intestinal Inflammation**

Fecal samples for assessment of fecal elastase-1, fecal calprotectin, and other markers of intestinal inflammation will be collected.

#### **11.5.6 Multiple Breath Washout**

MBW is optional and will only be performed on subjects for whom additional or separate informed consent was obtained. Also, MBW will only be performed at sites that are adequately trained and qualified and are equipped with a mass spectrometry MBW system. Therefore, only a subset of subjects will undergo MBW assessment. However, subjects from other sites may be referred to the sites that have capability to perform MBW. Detailed procedures for the MBW will be supplied in a separate study manual.

### **11.6 Safety**

Safety evaluations will include AEs, clinical laboratory assessments, clinical evaluation of vital signs, 12-lead ECGs, physical examinations (PEs; with clinically significant abnormalities recorded as medical history or adverse events), and OEs.

#### **11.6.1 Adverse Events**

All AEs will be assessed, documented, and reported in accordance with ICH GCP guidelines. Section 13.1 outlines the definitions; collection periods; criteria; and procedures for documenting, grading, and reporting AEs. A separate document that details AE CRF completion guidelines for investigators as well as training will be provided.

#### **11.6.2 Clinical Laboratory Assessments (Ivacaftor Arm Only)**

Blood samples for clinical laboratory assessments will be analyzed at a central laboratory. Local laboratories may be used at the discretion of the local investigator for management of urgent medical issues. If a local laboratory test value is found to be abnormal and clinically significant, it will be verified by the central laboratory as soon as possible after the investigator becomes aware of the abnormal result. The Vertex medical monitor or authorized designee should be notified. Specific instructions for the collection, processing, and shipment of samples will be provided in a separate Laboratory Manual. Laboratory test results that are abnormal and considered clinically significant will be reported as AEs (see Section 13.1).

The safety laboratory test panels are shown in [Table 11-1](#).

**Table 11-1 Safety Laboratory Test Panels**

Serum Chemistry	Hematology
Glucose	Hemoglobin
Blood urea nitrogen	Hematocrit
Creatinine	Red blood cell count
Sodium	Platelet count
Potassium	White blood cell count
Calcium	Differential (absolute and percent):
Phosphate	Eosinophils
Bilirubin, direct bilirubin	Basophils
Alkaline phosphatase	Neutrophils
Aspartate transaminase	Lymphocytes
Alanine transaminase	Monocytes
Lactate dehydrogenase	
Gamma-glutamyl transferase	
Protein	
Albumin	
Amylase	
Lipase	

Note: Screening Visit blood draws will be done after a minimum 4-hour fast. All subsequent blood draws do not require fasting.

### **CFTR Genotype:**

Subjects must have an approved ivacaftor-responsive mutation on at least 1 allele to meet inclusion criteria (see study manual and approved country/region ivacaftor label). The genotype results must be available before the first dose of study drug is administered to the subject. Subjects who had *CFTR* genotyping completed in Study 124 will not require repeat testing upon entry into this study.

If a genotype test has been performed previously and is documented in the subject's medical record, the subject's eligibility must be approved by the Vertex medical monitor.

If a historic genotype result is not available at screening or if the historic genotype result is not approved by the Vertex medical monitor, subjects will be tested for *CFTR* genotype and the results must be reviewed before the first dose of study drug.

Subjects will not receive the study drug if *CFTR* genotype is not confirmed by a historic genotype result OR by genotype testing at screening.

Instruction for collecting a sample for *CFTR* genotyping will be included in the Laboratory Manual.

### **Elevation of LFT Parameters:**

Subjects with new treatment-emergent ALT or AST elevations of  $>3 \times \text{ULN}$  must be followed closely, including repeat confirmatory testing performed by the central laboratory within 48 to 72 hours of the initial finding and subsequent close monitoring of ALT and AST levels, as clinically indicated. In addition, if ALT or AST levels are  $>5 \times \text{ULN}$ , repeat follow-up levels must be obtained within  $7 \pm 2$  days and followed up 7 days later. All reasonable efforts should be made for repeat confirmatory analysis by the central laboratory. If, under exceptional

circumstances, these blood samples must be drawn and/or analyzed at a local laboratory, approval must be first obtained from the Vertex medical monitor. Elevations in LFTs measured by the local laboratory must be reported immediately to the Vertex medical monitor, and the subject must have the tests repeated and sent to the central laboratory as soon as possible (ideally within 48 to 72 hours).

#### **LFT Elevations Leading to Study Drug Interruption:**

Study drug administration must be interrupted immediately and the Vertex medical monitor must be notified if any of the following criteria is met:

- ALT or AST  $>8 \times$  ULN, or
- ALT or AST  $>5 \times$  ULN for 2 weeks or more, or
- ALT or AST  $>3 \times$  ULN in association with elevation of bilirubin  $>2 \times$  ULN and/or clinical jaundice

Repeat testing should be performed within 48 to 72 hours to confirm the initial elevation.

A thorough investigation of potential causes should be conducted, and the subject should be followed closely for clinical progression.

If no convincing alternative etiology (e.g., concurrent infections) for the elevated transaminases is identified, regardless of whether ALT or AST levels have improved, the subject must be discontinued from the study in consultation with the Vertex medical monitor (Section 9.7). Subjects in whom treatment is discontinued for elevated transaminases should have their transaminases monitored closely until levels normalize or return to baseline.

If a convincing alternative cause of transaminase elevation has been identified, study drug may be resumed once transaminases return to  $\leq 2 \times$  ULN. Approval of the Vertex medical monitor is required before resumption of study drug. Upon resumption of study drug, transaminases should be assessed weekly for 4 weeks. If any protocol-defined transaminase elevation occurs within 4 weeks of rechallenge with the study drug (with confirmation of the initial elevation by repeat testing within 48 to 72 hours), then the study drug must be permanently discontinued, regardless of the presumed etiology.

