### **9.1.1.5 Ivacaftor Arm Early Termination of Treatment (All Subjects)**

Subjects who prematurely discontinue treatment before their last scheduled dose will be required to complete the ETT Visit, Safety Follow-up Visit, and Follow-up OE. The ETT Visit must be completed as soon as possible after the last dose of ivacaftor. If the ETT Visit occurs 3 weeks or later after the last dose of ivacaftor, the Safety Follow-up Visit will not be required.

Subjects who receive commercially available ivacaftor will be discontinued from ivacaftor dosing and will complete the ETT Visit and Follow-up OE; the Safety Follow-up Visit will not be required.

If the subject withdraws consent for the study, no further evaluations should be performed and no additional data should be collected. Vertex may retain and continue to use any data collected before such withdrawal of consent.

ETT assessments are listed in [Table 3-1](#) and [Table 3-2](#) for subjects from Study 124 Part B and [Table 3-3](#) for subjects not from Study 124 Part B.

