#### **9.7 Removal of Subjects**

Subjects may withdraw from the study at any time at their own request. Subjects may be withdrawn from study drug treatment at any time at the discretion of the investigator or Vertex for safety, behavior, noncompliance with study procedures, or administrative reasons. If a subject has been withdrawn from study drug treatment, the subject should continue to be followed through the ETT, Safety Follow-up, and OE Follow-up Visits, as indicated in Sections 9.1.1.3 and 9.1.1.5, provided the subject's parent or legal guardian has not withdrawn consent.

If a subject does not return for a scheduled visit, reasonable effort will be made to contact the subject's parent or legal guardian. In any circumstance, reasonable effort will be made to document subject outcome. The investigator will inquire about the reason for withdrawal, request that the subject's parent or legal guardian return all unused investigational product(s), request that the subject return for a Safety Follow-up Visit, if applicable (see Section 9.1.1.5), and follow up with the subject's parent or legal guardian regarding any unresolved adverse events (AEs).

If the subject's parent or legal guardian withdraws consent for the study, no further evaluations will be performed and no additional data will be collected. Vertex may retain and continue to use any data collected before such withdrawal of consent.

A subject **will be** discontinued from study treatment for any of the following reasons:

- Vertex, regulatory authorities, or the site's IRB or ethics committee (EC) closes the study.
- A subject is noncompliant with study protocol requirements, restrictions, and instructions to an extent that is considered unacceptable by the investigator or Vertex medical monitor.
- A subject participates in another interventional clinical study.
- A subject develops a new lens opacity or cataract (see Section 11.6.5).

A subject **may be** discontinued from study treatment, after discussion between the investigator and the Vertex medical monitor, for any of the following reasons:

- A subject develops a medical condition that requires prolonged concomitant therapy with a prohibited medication or prolonged interruption of ivacaftor.
- A subject develops a life-threatening adverse event or a serious adverse event (SAE) that places them at immediate risk.
- A subject has an increase in liver function test levels (LFTs; e.g., AST or ALT levels) as described in Section 11.6.2.

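### Protocol 11.6.2 and 9.7 disagree on whether discontinuation for raised liver tests is mandatory or discretionary, and on whether it is from the study or from study treatment

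*Protocol*

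**What the plan says.** Protocol 11.6.2 (LFT Elevations Leading to Study Drug Interruption) requires immediate interruption, and notification of the medical monitor, in three situations: ALT or AST above 8 × ULN; above 5 × ULN for 2 weeks or more; or above 3 × ULN with bilirubin above 2 × ULN and/or clinical jaundice. It then gives two rules for stopping for good.

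- Unexplained elevation. The condition is "If no convincing alternative etiology (e.g., concurrent infections) for the elevated transaminases is identified, regardless of whether ALT or AST levels have improved". The consequence is "the subject must be discontinued from the study in consultation with the Vertex medical monitor", with a reference to Section 9.7.
- Recurrence on rechallenge. If a protocol-defined elevation occurs within 4 weeks of restarting and is confirmed, "then the study drug must be permanently discontinued, regardless of the presumed etiology".

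Section 9.7 (Removal of Subjects) has two lists of reasons for stopping study treatment. The mandatory list has four entries: closure of the study, unacceptable noncompliance, entry into another interventional study, and a new lens opacity or cataract. The discretionary list opens with "A subject may be discontinued from study treatment, after discussion between the investigator and the Vertex medical monitor" and includes "A subject has an increase in liver function test levels (LFTs; e.g., AST or ALT levels) as described in Section 11.6.2".

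On follow-up, Section 9.1.1.5 says "Subjects who prematurely discontinue treatment before their last scheduled dose will be required to complete the ETT Visit, Safety Follow-up Visit, and Follow-up OE".

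**The concern.** A site that starts in 11.6.2 is told that it must discontinue. If it follows the reference to 9.7, it reaches a list that leaves the decision to discussion, and the liver-test entry there sends it back to 11.6.2. Two liver-test stops that 11.6.2 words as mandatory are absent from the protocol's list of mandatory reasons. The object of the action changes as well: the study in one section, study treatment in the other.

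Safety is the primary objective of the ivacaftor arm, so the same liver signal should be handled and coded in one way. At stake are three things: whether stopping is required or optional, how the subject is counted in the disposition table, and whether a subject who continues on drug is a protocol deviation.

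**Working it through.** No figure in the plan bears on this and there is nothing to compute. The check is a comparison of texts.

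| Question | Protocol 11.6.2 | Protocol 9.7 |
|---|---|---|
| Force, unexplained elevation | *must*, in consultation with the medical monitor | *may be*, after discussion with the medical monitor |
| Force, recurrence on rechallenge | *must*, whatever the cause | no separate entry; covered only by the *may be* item |
| Scope | the study (unexplained); study drug (rechallenge) | study treatment |
| Liver-test item on the mandatory list | not applicable | none |

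**Step 1: force.** The 9.7 item does not use the word unexplained. It takes in every liver-test increase that 11.6.2 describes, including those with another cause where drug may be resumed. A discretionary word fits that wider group. It does not fit the two subsets for which 11.6.2 says *must*, and 9.7 has a mandatory list on which they could have been placed. The disagreement on force is therefore in the text for both subsets.

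**Step 2: scope.** The sentence after the unexplained-elevation rule reads "Subjects in whom treatment is discontinued for elevated transaminases should have their transaminases monitored closely until levels normalize or return to baseline". So 11.6.2 moves from the study to treatment within two sentences, and later to study drug. Elsewhere the documents keep these terms apart. SAP 8.2.1 counts premature discontinuation of treatment and premature discontinuation of the study as separate categories, each with its reason.

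**Step 3: follow-up.** The relevant texts are these.

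- Section 9.1.1.5 is headed for all subjects and is triggered by stopping treatment early. A subject removed for liver tests meets that trigger.
- Section 9.7, in its opening paragraph, keeps subjects withdrawn from study drug through the ETT, Safety Follow-up and Follow-up OE visits unless consent is withdrawn.
- Section 9.1.1.4 sets the Follow-up OE, 24 weeks (+ 14 days) after the last dose, for all subjects.
- Section 13.1.1.3 collects adverse events to about 4 weeks after the last dose even without a Safety Follow-up Visit, or to an ETT Visit held at 3 weeks or later if that comes first.
- The end of Section 9.7 describes what follows when subjects are discontinued from the study, in a different situation (approval declined, or no dose for an age cohort). It names the ETT and Safety Follow-up visits and does not mention the Follow-up OE.

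Most of these texts point to follow-up continuing. Only the last leaves a gap, and only for the Follow-up OE.

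**Step 4: later corrections.** SAP 2.1 reports two administrative letters. The one of 31 October 2017 concerns ECG visits. The one of 07 October 2022 revises 9.1.1.4, 9.1.1.5 and 9.7 for subjects who move to commercial ivacaftor, with minor clarifications on dose determination at Week 96 and an endpoint name. Neither touches the liver-test wording.

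**Step 5: analysis.** SAP 8.2.6 lists staying in the study after meeting withdrawal criteria as a potential important protocol deviation. For a subject with an unexplained elevation who goes on with treatment, 11.6.2 implies that the criterion was met, and 9.7 implies that it need not have been.

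**The case against.** The strongest reply is that the specific text governs the general one. Section 9.7 points to 11.6.2 for the particulars, and Section 9.6 does the same for interruptions. On that reading the *may be* entry is only a pointer, and the firmer instruction in 11.6.2 holds for its subset. This is a fair reading, and many sites would adopt it. It is not stated, however, and the reference in 11.6.2 runs the other way, to a section that assigns the event to discretion.

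Second, variation between sites is limited. Both routes involve the medical monitor, and 11.6.2 requires immediate interruption once a criterion is met. This stands: dosing is halted at that point in any case, and the disagreement concerns final discontinuation. Consultation does not settle whether that step is required.

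Third, a reader might infer from the words about leaving the study that 11.6.2 ends safety and ocular follow-up for infants with a suspected drug-related event. The documents do not support that. The next sentence of 11.6.2 orders transaminase monitoring, the visit requirements of 9.1.1.4, 9.1.1.5 and 9.7 apply on their own terms, and adverse events are collected to about 4 weeks after the last dose. In 9.1.1.5 and 9.7 the stated trigger for ending all evaluations is withdrawal of consent.

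**Conclusion.** This is an internal inconsistency in the protocol, real on force and on scope. It should be corrected because it concerns a stopping instruction for a liver signal in a trial whose primary endpoint is safety.

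Its size is modest. It applies to subjects who meet an interruption criterion with no other cause found, or whose elevation recurs within 4 weeks of rechallenge. The documents give no count of either. For each such subject the open points are the 24-week Follow-up OE, the disposition category, and deviation status.

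A reader might also put the cost at up to 24 weeks of lost follow-up per subject. That is not supported. After the Safety Follow-up Visit, about 4 weeks after the last dose, the schedule plans only the Follow-up OE and ocular adverse events, and 9.1.1.4 and 9.1.1.5 indicate that this examination is still due.

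The conclusion rests on the current protocol text and on the letters as reported in the SAP. The study manual and the deviation rules were not available and could already settle part of it. No view is taken on which clinical rule is right.

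**What to change.** Reconcile Sections 9.7 and 11.6.2 so that each liver-test event (unexplained elevation, and recurrence on rechallenge) carries the same instruction in both places, on force and on scope. Use one term for what is discontinued throughout 11.6.2. Confirm expressly that the ETT Visit, Safety Follow-up Visit and Follow-up OE of 9.1.1.5 apply to these subjects, or say otherwise. Then state in the SAP which disposition category of 8.2.1 these subjects enter, and align the important protocol deviation rules, which 8.2.6 says are finalized before database lock. The clinical content is for the sponsor to decide.

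The cost is protocol wording or an administrative letter, a route already used for 9.1.1.4, 9.1.1.5 and 9.7, plus a line in the SAP and in the deviation rules. It adds no visits or procedures to those already planned.
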